8.3.6. Disease-Related Events and/or Disease-Related Outcomes Not Qualifying as AEs or SAEs

Not applicable

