8.4. Treatment of Overdose

The anticipated pattern of events or symptoms following intentional or accidental overdose with safinamide is that related to its pharmacodynamic profile (MAO-B inhibition with activity dependent inhibition of sodium channels). The symptoms of excessive MAO-B inhibition (increase in dopamine level) could include hypertension, postural hypotension, hallucinations, agitation, nausea, vomiting and dyskinesia.

There is no known antidote to safinamide or any specific treatment for a safinamide overdose. If a significant overdose should occur, safinamide treatment should be discontinued and supportive treatment should be administered as clinically indicated.

In the event of an overdose, the Investigator should:

1. Contact the Medical Monitor immediately.
2. Closely monitor the participant for any AE/SAE or laboratory abnormalities
3. Obtain a plasma sample for PK analysis if requested by the Medical Monitor (determined on a case-by-case basis).
4. Document the quantity of the excess dose as well as the duration of the overdose in the CRF.

Decisions regarding dose interruptions or modifications will be made by the investigator in consultation with the Medical Monitor based on the clinical evaluation of the participant.

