- Any abnormal laboratory test results (hematology, clinical chemistry, or urinalysis) or other safety assessments (eg, ECG, radiological scans, vital signs measurements), including those that worsen from baseline, considered clinically significant in the medical and scientific judgment of the investigator (ie, not related to progression of underlying disease).
- Exacerbation of a chronic or intermittent pre-existing condition including either an increase in frequency and/or intensity of the condition.
- New conditions detected or diagnosed after study intervention administration even though it may have been present before the start of the study.
- Signs, symptoms, or the clinical sequelae of a suspected drug-drug interaction.
- Signs, symptoms, or the clinical sequelae of a suspected overdose of either study intervention or a concomitant medication. Overdose per se will not be reported as an AE/SAE unless it is an intentional overdose taken with possible suicidal/self-harming intent. Such overdoses should be reported regardless of sequelae.
- "Lack of efficacy" or "failure of expected pharmacological action" per se will not be reported as an AE or SAE. Such instances will be captured in the efficacy assessments. However, the signs, symptoms, and/or clinical sequelae resulting from lack of efficacy will be reported as AE or SAE if they fulfil the definition of an AE or SAE.
- The signs, symptoms, and/or clinical sequelae resulting from lack of efficacy will be reported as AE or SAE if they fulfil the definition of an AE or SAE. Also, "lack of efficacy" or "failure of expected pharmacological action" also constitutes an AE or SAE.

Events NOT Meeting the AE Definition

- Any clinically significant abnormal laboratory findings or other abnormal safety assessments which are associated with the underlying disease, unless judged by the investigator to be more severe than expected for the participant's condition.
- The disease/disorder being studied or expected progression, signs, or symptoms of the disease/disorder being studied, unless more severe than expected for the participant's condition.
- Medical or surgical procedure (eg, endoscopy, appendectomy): the condition that leads to the procedure is the AE.
- Situations in which an untoward medical occurrence did not occur (social and/or convenience admission to a hospital).

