- Anticipated day-to-day fluctuations of pre-existing disease(s) or condition(s) present or detected at the start of the study that do not worsen.

Definition of SAE

If an event is not an AE per definition above, then it cannot be an SAE even if serious conditions are met (eg, hospitalization for signs/symptoms of the disease under study, death due to progression of disease).

A SAE is defined as any untoward medical occurrence that, at any dose:

a. Results in death

b. Is life-threatening

The term 'life-threatening' in the definition of 'serious' refers to an event in which the participant was at risk of death at the time of the event. It does not refer to an event, which hypothetically might have caused death, if it were more severe.

c. Requires inpatient hospitalization or prolongation of existing hospitalization

In general, hospitalization signifies that the participant has been detained (usually involving at least an overnight stay) at the hospital or emergency ward for observation and/or treatment that would not have been appropriate in the physician's office or outpatient setting. Complications that occur during hospitalization are AEs. If a complication prolongs hospitalization or fulfills any other serious criteria, the event is serious. When in doubt as to whether "hospitalization" occurred or was necessary, the AE should be considered serious.

Hospitalization for elective treatment of a pre-existing condition that did not worsen from baseline is not considered an AE.

d. Results in persistent disability/incapacity

- The term disability means a substantial disruption of a person's ability to conduct normal life functions.
- This definition is not intended to include experiences of relatively minor medical significance such as uncomplicated headache, nausea, vomiting, diarrhea, influenza, and accidental trauma (eg, sprained ankle) which may interfere with or prevent everyday life functions but do not constitute a substantial disruption.

e. Is a congenital anomaly/birth defect

f. Other situations:

- Medical or scientific judgment should be exercised in deciding whether SAE reporting is appropriate in other situations such as important medical events that may not be immediately life-threatening or result in death or hospitalization but may jeopardize the participant or may require medical or surgical intervention to prevent one of the other outcomes listed in the above definition. These events should usually be considered serious.

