11.1.8. Death

All subjects who have an AE with an outcome of ‘Death’ will be presented in a listing using the Safety Set.

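### Deaths and admissions judged to be expected Parkinson's disease can fall outside AE and SAE reporting, and the SAP death listing draws only on AE records

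*Protocol*

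**What the plan says.** Protocol Appendix 3 (10.3) works in two steps. First, among events that do not meet the AE definition, it places the disease itself and "expected progression, signs, or symptoms of the disease/disorder being studied, unless more severe than expected for the participant's condition". Second, the SAE definition opens with the rule "If an event is not an AE per definition above, then it cannot be an SAE even if serious conditions are met", and its examples are "hospitalization for signs/symptoms of the disease under study, death due to progression of disease". The same appendix has a provision that pulls the other way, counting as an AE "Exacerbation of a chronic or intermittent pre-existing condition including either an increase in frequency and/or intensity of the condition".

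Protocol 8.3.6 has the heading "Disease-Related Events and/or Disease-Related Outcomes Not Qualifying as AEs or SAEs". Its whole body is a statement that the section does not apply.

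SAP 11.1 and 11.1.4 define AEs and SAEs without any disease-related exclusion. In 11.1.4, any untoward occurrence that results in death or requires admission is an SAE.

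The death listing in SAP 11.1.8 covers "All subjects who have an AE with an outcome of" death, so it needs an AE record to pick up a case. The overview in SAP 11.1 likewise counts AEs leading to death. SAP 6.1 summarises reasons for study discontinuation by treatment group, with death as a category separate from adverse event.

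**The concern.** Three places in the plan handle serious disease-related events differently. Appendix 3 lets some of them drop out of AE and SAE status, 8.3.6 identifies none, and the SAP definition excludes none. Whether a death or admission counts as a safety event can then depend on the investigator's view of what was expected for that patient, and on which text the site has in mind.

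The SAP outputs inherit that judgement. A reader of the safety section would normally take the death listing as complete. As specified, it is complete only for deaths that were first accepted as AEs. At stake is the completeness of the gravest safety information by arm, in a trial with no data monitoring committee (Protocol 9.5.1).

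**Working it through.** The plan states no figure on this point, so the check traces an event through the text.

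**Step 1: is it an AE?** Under Appendix 3, an event that is an expected sign, symptom or progression of Parkinson's disease is not. If it is more severe than expected for that participant, it is. The exacerbation provision also brings in worsening in frequency or intensity.

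**Step 2: can it be an SAE?** Under Appendix 3, only if it passed step 1. Under SAP 11.1.4, read alone, any fatal or hospitalised occurrence qualifies.

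**Step 3: which SAP outputs show it?** The table takes Appendix 3 as applied by the site and the SAP as programmed from its text.

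| SAP output | Death judged expected progression | Admission judged expected disease | Event judged worse than expected |
|---|---|---|---|
| TEAE tables (11.1, 11.1.1) | absent | absent | present if treatment-emergent |
| SAE tables and listing (11.1.4) | absent | absent | present if serious |
| Overview row, AEs leading to death (11.1) | absent | not relevant | present if fatal |
| Death listing (11.1.8) | absent | not relevant | present if fatal |
| TEAEs leading to study discontinuation (11.1.6) | absent: needs adverse event as the termination reason | absent | present if that is the reason |
| Disposition (6.1) | counted by arm under death | no category for an admission | depends on the reason recorded |

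The first column leaves one trace, a disposition count with its listing, outside the safety section. The second leaves no trace in any safety output.

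**Step 4: scale of one event.** Protocol 9.2 plans 105 randomised. At 2:1 that is 105 × 2/3 = 70 active and 105 × 1/3 = 35 placebo. One missing event moves an arm's percentage by 1/70 = 1.4 points or 1/35 = 2.9 points. This shows only what one event weighs. The number of such events cannot be derived, because neither document gives an SAE, death or admission rate.

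**The case against.** The case against has several good parts.

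- **8.3.6 may be an unused template heading.** Protocol 7.1, on discontinuing study intervention, is marked not applicable in the same way, yet Sections 8 and 8.4 and Appendix 4 all provide for stopping treatment. Protocol 8.3 and 8.3.1 send sites to Appendix 3 for definitions and procedures. A reader might infer that 8.3.6 positively rules out any exemption, but its text does not say that. The mismatch between Appendix 3 and SAP 11.1.4 remains under either reading.
- **The exclusion is limited.** A reader might infer that Appendix 3 bars every admission or death attributed to Parkinson's disease. It does not. Events more severe than expected are AEs, and so are exacerbations.
- **The population limits what is left.** Patients are Hoehn and Yahr stage 2-3, have an MMSE of at least 24, are free of severe dyskinesia, and are treated for 16 weeks. Few unplanned admissions or deaths from the disease would plausibly be judged expected.
- **Deaths do not disappear.** Disposition counts them by arm, and Appendix 3 asks for post-mortem findings for any participant who dies. But a disposition count is not a death listing, and no SAP output uses the post-mortem findings.
- **The overdose list is weak evidence.** Protocol 8.4 names "hypertension, postural hypotension, hallucinations, agitation, nausea, vomiting and dyskinesia", and a reader might infer that effects at the trial dose are being coded as disease. That list describes overdose, and Appendix 3 makes the signs and symptoms of a suspected overdose AEs.

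A reader might also infer that one or two omissions could reverse the safety comparison. With no event rate in the documents and only descriptive safety analyses (Protocol 9.4.2), nothing supports this.

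These points limit the size of the problem. They do not close the gap in the death listing.

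**Conclusion.** The point holds in a limited form. Deaths and admissions judged to be expected Parkinson's disease, and not more severe than expected, can fall outside AE and SAE reporting. The SAP then shows such a death only in disposition and such an admission in no safety output. The passages are not reconciled with one another.

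The effect cannot be quantified and is probably small in this population over 16 weeks. The case for change rests on completeness at almost no cost, not on a demonstrated bias.

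The conclusion assumes that sites apply Appendix 3 as written, that the outputs are programmed from the SAP text, and that a death not accepted as an AE is still entered on the Study Completion/Termination page named in SAP 11.1.6.

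**What to change.** 1. Reconcile the AE exclusion, the exacerbation provision and the SAE rule in Appendix 3 with Protocol 8.3.6 and SAP 11.1.4, and tell sites in one clarification which text governs.
2. Amend SAP 11.1.8 along these lines: *All deaths in the Safety Set will be listed, and counted by treatment group, using every death recorded on the AE or SAE pages or on the Study Completion/Termination page, whatever the attributed cause.*

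The cost is one clarification to sites and one further data source for an existing listing, plus a short count.

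A listing of every admission regardless of attribution is not proposed. The Schedule of Activities has no item that collects an admission without an AE record, so it would need new data collection. For admissions, the clarification in item 1 is the proportionate remedy.

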10.4. Appendix 4: Contraceptive Guidance and Collection of Pregnancy Information

Definitions:

Woman of Childbearing Potential (WOCBP)

A woman is considered fertile following menarche and until becoming post-menopausal unless permanently sterile (see below).

Women in the following categories are not considered WOCBP

1. Premenarchal
2. Premenopausal female with 1 of the following:
 - Documented hysterectomy
 - Documented bilateral salpingectomy
 - Documented bilateral oophorectomy

Note: Documentation can come from the site personnel's: review of the participant's medical records, medical examination, or medical history interview.

3. Postmenopausal female
 - A postmenopausal state is defined as no menses for 12 months without an alternative medical cause. A high follicle stimulating hormone (FSH) level in the postmenopausal range may be used to confirm a postmenopausal state in women not using hormonal contraception or hormonal replacement therapy (HRT). However, in the absence of 12 months of amenorrhea, a single FSH measurement is insufficient.
 - Females on HRT and whose menopausal status is in doubt will be required to use one of the non-estrogen hormonal highly effective contraception methods if they wish to continue their HRT during the study. Otherwise, they must discontinue HRT to allow confirmation of postmenopausal status before study enrollment.

Contraception Guidance:

Female participants

Female participants of childbearing potential are eligible to participate if they agree to use a highly effective method of contraception consistently and correctly as described in Table 2.

Table 2 Highly Effective Contraceptive Methods

| Highly Effective Contraceptive Methods That Are User Dependent^a Failure rate of <1% per year when used consistently and correctly. |
|---|
| Combined (estrogen and progestogen containing) hormonal contraception associated with inhibition of ovulation 
• Oral• Intravaginal• Transdermal |
| Progestogen only hormonal contraception associated with inhibition of ovulation 
• Oral• Injectable |
| Highly Effective Methods That Are User Independent^a |
| Implantable progestogen only hormonal contraception associated with inhibition of ovulation 
• Intrauterine device (IUD)• Intrauterine hormone-releasing system (IUS)• Bilateral tubal occlusion |
| Vasectomized partner |
| A vasectomized partner is a highly effective contraception method provided that the partner is the sole male sexual partner of the WOCBP and the absence of sperm has been confirmed. If not, an additional highly effective method of contraception should be used. |
| Sexual abstinence |
| Sexual abstinence is considered a highly effective method only if defined as refraining from heterosexual intercourse during the entire period of risk associated with the study intervention. The reliability of sexual abstinence needs to be evaluated in relation to the duration of the study and the preferred and usual lifestyle of the participant. |
| NOTES: |
| a) Typical use failure rates may differ from those when used consistently and correctly. Use should be consistent with local regulations regarding the use of contraceptive methods for participants participating in clinical studies. |

Pregnancy Testing:

- WOCBP should only be included after a confirmed menstrual period and a negative highly sensitive urine pregnancy test.
- Pregnancy testing will be performed whenever a menstrual cycle is missed or when pregnancy is otherwise suspected

Collection of Pregnancy Information:

Female Participants who become pregnant

- The investigator will collect pregnancy information on any female participant who becomes pregnant while participating in this study. Information will be recorded on the appropriate form and submitted to the sponsor within 24 hours of learning of a participant's pregnancy. The participant will be followed to determine the outcome of the pregnancy. The investigator will collect follow-up information on the participant and the neonate and the information will be forwarded to the sponsor. Generally, follow-up will not be required for longer than 6 to 8 weeks beyond the estimated delivery date. Any termination of pregnancy will be reported, regardless of fetal status (presence or absence of anomalies) or indication for the procedure.
- While pregnancy itself is not considered to be an AE or SAE, any pregnancy complication or elective termination of a pregnancy will be reported as an AE or SAE. A spontaneous abortion is always considered to be an SAE and will be reported as such. Any post-study pregnancy related SAE considered reasonably related to the study intervention by the investigator will be reported to the sponsor as described in Section 8.3.4. While the investigator is not obligated to actively seek this information in former study participants, he or she may learn of an SAE through spontaneous reporting.
- Any female participant who becomes pregnant while participating in the study will discontinue study intervention and be withdrawn from the study.

10.5. Appendix 9: Abbreviations

| Abbreviation | Definition |
|--------------|--|
| ADR | Adverse drug reaction |
| AE | Adverse event |
| ANCOVA | Analysis of covariance |
| CA | Competent Authority |
| CGI | Clinical Global Impression |
| CGI-C | Clinical Global Impression of Change |
| CGI-S | Clinical Global Impression of Severity |
| COMT | Catechol-O-methyltransferase |
| CR | Controlled release |
| CRF | Case report form |
| CRO | Contract research organization |
| EC | Ethics Committee |
| ECG | Electrocardiogram |
| EDC | Electronic data capture |
| eCRF | Electronic case report form |
| EMA | European Medicines Agency |
| EOT | End of treatment |
| ePRO | Electronic patient reported outcomes |
| ET | Early termination |
| FAS | Full analysis set |
| GCP | Good Clinical Practice |
| HADS | Hospital Anxiety and Depression Scale |

| | |
|-----------|--|
| HIV | Human immunodeficiency virus |
| ICH | International Conference on Harmonization (now International Council on Harmonization) |
| IMP | Investigational medicinal product |
| IPD | Idiopathic Parkinson's Disease |
| IR | Immediate release |
| IWRS | Interactive web response system |
| L-Dopa | Levodopa |
| LOCF | Last observation carried forward |
| MAO-B | Monoamine oxidase-B |
| MAOI | Monoamine oxidase inhibitor |
| MDS-UPDRS | Movement Disorder Society - Unified Parkinson's Disease Rating Scale |
| MedDRA | Medical Dictionary for Regulatory Activities |
| mg | Milligrams |
| mL | Millilitres |
| MMSE | Mini-mental State Examination |
| NRS | Numerical Rating Scale |
| NSAIDs | Nonsteroidal anti-inflammatory drugs |
| od | Once daily |
| PD | Parkinson's Disease |
| PGI | Patient Global Impression |
| PGI-C | Patient Global Impression of Change |
| PGI-S | Patient Global Impression of Severity |
| PP | Per protocol |

| | |
|--------|--|
| PT | Preferred term |
| SA | Safety analysis |
| SAE | Serious adverse event |
| SAP | Statistical analysis plan |
| SAR | Serious adverse reaction |
| SETTLE | Safinamide Treatment as add-on To LEvodopa in idiopathic Parkinson's disease with motor fluctuations |
| SOC | System organ class |
| SOP | Standard operating procedures |
| SSRI | Selective serotonin reuptake inhibitor |
| SUSAR | Suspected unexpected serious adverse reaction |

10.6. Appendix 10: Contingency Plan

Zambon PAIN study Coronavirus (2019-nCoV)

Contingency Plan - V7 – 07 April 2020

Study Code: Z7219M01

EUDRACT number : 2017-002426-20

Background and Rationale

CDC is closely monitoring an outbreak of respiratory illness caused by a novel (new) coronavirus (named “2019-nCoV”) that was first detected in Wuhan City, Hubei Province, China and which continues to expand. On January 30, 2020, the International Health Regulations Emergency Committee of the World Health Organization declared the outbreak a “public health emergency of international concern” and subsequently on March 11, 2020 the pandemic status has been declared. Coronaviruses are a large family of viruses that are common in many different species of animals, including camels, cattle, cats, and bats. Rarely, animal coronaviruses can infect people and then spread between people such as with MERS, SARS, and now with 2019-nCoV.

In response to this outbreak, many restrictions have been implementing by government and health departments in the affected countries. These restrictions include but are not limited to the establishment of quarantine zones, recommended self-quarantine periods, and travel restrictions. To mitigate the impact of such restrictions on the conduct of these studies and ensure the safety and wellbeing of participating patients and investigator sites, as well support patient retention and maintain data integrity, the following plan has been created.

1. Close monitoring of the contingency and monitoring activities

In the agenda of the study regular calls between Zambon and CRO, a specific item for discussion should be added aimed at sharing for each of the countries involved in the study the current status of the coronavirus emergency (government recommendations, any specific restriction in the areas of the study sites) covering:

- impacts on the study enrolment/patients' visit at site: for this topic please refers to sections 2 and 3)

- impacts on monitoring activities: for this topic, on top of what is reported in section 2, please note that Zambon should be informed about any CRO's restrictions in performing visit activities at site; all the efforts should be spent to respect the monitoring visit frequency as per Monitoring Plan; deviations should be documented and approved by Sponsor. The Monitoring plan will be updated and will reflect the new conditions for the micro-management. The updated monitoring Plan will be approved by Zambon.

2. Communication with site

Ongoing communication with the PI/site should happen according to the study specific frequency agreed with Zambon until the concerned site continues activity under standard working conditions. The frequency of the communications should be increased after agreement with the Zambon if the status at site changes.

Topics to be discussed during the calls (on top of the standard ones):

- Investigate any potential issue related to coronavirus outbreak
- Health status of patients (AE/SAE recording)
- Inform the PI/site of any delay to planned SIV or MV.
- Confirm with the PI/sites whether or not they plan to continue enrolling new patients.
- Perform remote motoring (details will be in the MP)
- For sites with ongoing patients, please see next section.

3. Sites with ongoing patients:

Wherever possible, every effort should be made to have the patient attend the hospital for their on site study visits according to the schedule in the protocol.

During the contact with sites please consider the following options that should be discussed case by case and approved by Zambon prior to implementation:

- If the patient does not want to go the hospital for the visit or they are not allowed by local authorities, the following can be explored with the site in order to maintain patient retention and then feedback to Sponsor for approval:
 - Recommend patients to use private car/driver or to pay a taxi for the on site visits. Costs will be reimbursed upon the evidence of receipts;

- Decide whether assessment might be performed via phone call like for example interviewing patients about general health conditions (Adverse Event, Concomitant Medication) and collection of vital signs using patient's domestic equipment (if feasible). The study's e-questionnaires MDS-UPDRS, CGI-s and CGI-c to be completed by the site staff at specific study visits through the study device might be compiled during the phone call. In case of site inability in using the site-based device, the site staff might make use of the paper version of the e-questionnaires which will be provided by the Sponsor.

The data collected through the paper form will then be transferred into the specific study database via data correction form. This will also be documented in medical charts and paper forms retained as source document.

- Patient verbal consent to continuing in the study and to being contacted by site staff via phone call will be documented in medical charts as well as the details of which assessment have been done via phone call and with which equipment and method

b) If the clinic location where study visits are routinely performed is not available due to the Coronavirus outbreak (e.g. closed, being utilized for non-study purposes, etc.), sites may conduct study visits at a suitable alternative location and lab samples can be taken and analysed from the local lab of the alternative site (every effort should be spent to collect normal ranges). In such case, it should first be checked if there is any regulatory or ethical implication for involving an alternative location.

c) Confirm with the site if it is permitted by the EC/GCP/local authorities to send study drug directly to the patient's home. If the study drug is to be sent to patient's home, the patient must also confirm their agreement for the courier to be provided with their name and address for shipping purposes. This confirmation will be documented in the patient's source notes. The patient's name and address will not be provided to any other parties (e.g. Sponsor, CRO, vendor, etc.). Upon receipt of study drug, the patient should promptly inform the site staff if the drug has been received in good condition. Site staff need to document the entire process from site to home in the patient chart.

Site can also explore if a patient's care-giver is willing to go at site to pick up the IMP.

Details will be given at sites case by case according to the recommendation coming from regulatory/local authorities.

d) Where required, patient visits may be changed beyond the maximum visit window permitted in the current approved protocol. The permissible duration of any delay will be assessed on a case by case basis and supported by a phone call between PI/study staff and

patient in order to assess any potential adverse events (AEs), whether the patient has sufficient study supplies and to confirm the patient's status and wellbeing. Patients will continue on study treatment at home during this extension and the site is authorised to allow subjects to administer the additional tablets present in the wallet that are in the 'grey colored slots' and that are marked as Do Not Take in the IP label. As confirmed by Almac (CMO responsible for IP secondary packaging) the tablets in those slots can be dispensed in the same manner as for the other tablets in the wallet and there are no blinding concerns

- Patient verbal consent to continuing in the study and to being contacted by site staff via phone call will be documented in medical charts.
- All decisions regarding patient re-scheduling and follow-up must be clearly documented in the patient's source notes.
- The CRA will document all patient visits performed outside of the protocol defined visit window as protocol deviations, referencing this contingency plan.
- In cases where approval is given to extend home-treatment for a patient, and they do not have sufficient IMP to enable continued treatment until the rescheduled visit date, the site will ship additional IMP to the patient (please refer to paragraph 3c). If not feasible, Zambon may consider with ALMAC the IMP delivery at patient home. Details will be given at sites case by case according to the recommendation coming from regulatory/local authorities. For IMP shipping from site to patient home, a dedicated courier appointed by the Sponsor/CRO/site will be involved and a data privacy infographic for the subject will be included in the shipping packaging either by site pharmacist or directly by the appointed courier

e) At the end of the 2019-nCoV emergency and when it will be possible to reach the site, the subject or caregiver/familiar will return the IP and eDiaries to site at the earliest opportunity. The site staff will ensure it and will document it in the patient's source document

11. References

